17 DATA MANAGEMENT

17.1 DATA COLLECTION

This study will enroll healthy volunteers. For this reason, study data will not be collected in hospital medical records but rather as follows:

- 1. Subject data, including the date when the Informed Consent is signed, subject demographics, screening test results (printouts of laboratory results signed by the Principal Investigator), patient eligibility, adverse events and any other measurements will be collected on paper CRFs, which will be signed by the Principal Investigator after completion.
- 2. Measurements obtained with the BrOxy M: the photoplethysmographic signals recorded during the measurements are stored on a magnetic support (hard disk of the PC used for the BrOxy M software). The files will contain:
 - a. The recorded values of the red and infrared sensors integrated in BrOxy M, acquired with a constant frequency over time and stored continuously until the measurement is stopped;
 - b. The time when the registration is started;
 - c. The values of the accelerometric sensor integrated in BrOxy M, recorded in parallel to the photoplethysmographic signals;
- 3. Measurements obtained with the reference device Nellcor™ mod. PM1000N. The files will contain:
 - a. The time when each sample is recorded;

Clinical Investigational Plan			
Protocol No.:	Version 1.0	Page 37 of 45	
01M2020-CH.LMD	Date: 22 December 2020	Page 57 01 45	

b. SpO₂ measurements

c. HR measurements

17.2 DEFINITION OF VALID MEASUREMENT

A "valid measurement" is defined as a measurement obtained under the following conditions:

- 1. Signal compliant with quality control for both the reference and BrOxy M
- 2. No movement above predefined threshold for both the reference and BrOxy M

The quality control of the signal is carried out automatically by the HR and SpO₂ calculation algorithm and is based on the following conditions:

- 1. Starting from the signals, through appropriate band-pass filters, the following components are calculated as follows:
 - a. RED_DC = continuous part of the red signal;
 - b. RED_AC = alternating part of the red signal;
 - c. IR_DC = continuous part of the infrared signal;
 - d. IR_AC = alternating part of the infrared signal
- 2. Average values of RED_DC and IR_DC have to be in the expected range, determined empirically;
- 3. If the previous point occurs, peak-peak amplitude values of RED_AC and IR_AC have to be in the empirically determined acceptability range;
- 4. If the previous condition is verified, the correlation coefficient calculated between IR_AC and IR_AC has to be higher than the empirically determined threshold;

The algorithm used to recognize the time windows to be excluded for motion artifacts is organized with the following steps:

- 1. Control of the amplitude of photoplethysmographic signals: the amplitude of the alternating component of red and infrared signals (obtained by filtering signals with an anti-causal high pass filter must not exceed a threshold determined empirically;
- 2. Control of the correlation between photopletismographic signals and accelerometric signals: the module of accelerometric signals recorded on three orthogonal axes of space (A_x,A_y and A_z) is calculated as $|A_{XYZ}[t]| = \sqrt{A_x[t]^2 + A_y[t]^2 + A_z[t]^2}$ and, subsequently, it occurs that:
 - a. The correlation between and $|A_{XYZ}[t]|$ plethythygraphic signal recorded in the red frequency is less than a certain threshold derived empirically;
 - b. The correlation between $|A_{XYZ}[t]|$ and plethythygraphic signal recorded in the infrared frequency is less than a certain threshold derived empirically;
- 3. If the conditions in point 1 and 2 occur, the time window from which to derive heart rate and SpO_2 data is excluded from the collection of data deemed useful in the context of the study.

Clinical Investigational Plan			
Protocol No.:	Version 1.0	D 20 -f 45	
01M2020-CH.LMD	Date: 22 December 2020	Page 38 of 45	

At this point, once all the above conditions are verified, the values of SpO_2 and HR are calculated for the signal windows considered. These values are considered acceptable if the following conditions occur at the same time:

- Heart rate values between 40 and 280 bpm
- SpO₂ values between 80 and 100 %

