 SpO₂ and HR values corresponding to the same time points selected for the reference device will
 be chosen.

Clinical Investigational Plan		
Protocol No.:	Version 1.0	Page 16 of 45
01M2020-CH.LMD	Date: 22 December 2020	1 486 10 01 13

As a result, it is expected that from each enrolled subject up to 32 paired measurements of SpO_2 and HR will be obtained from the reference device and BrOxy M. Table 1 below summarises the data collection process.

Plateau no.	Range SpO₂ (%)	Inhaled solution	Plateau duration	No. of Measurements of SpO ₂ and HR extracted from recordings
1)	95 – 100 (target 97%)	Ambient air (medical air)	2.5'	8
II)	90 – 94 (target 92%)	O2 15% + N 85%	2.5'	8
III)	85 – 89 (target 87%)	O2 13% + N 87%	2.5'	8
IV)	80 – 84 (target 82%)	O2 11% +N 89%	2.5'	8
			Total	32 measurements

Table 1: Number of measurements to be performed for each subject, for each target level of SpO₂ and indication of the gaseous solution inhaled during each target level.

After completing the study on 10 subjects, collecting around 320 paired measurements it will be verified that, by dividing the desaturation interval into three equal parts, each part contains around a third of the measurements made. Therefore, considering the minimum target number of 200 measurements (per EN 80601-2-61 standard) and the interval between 98% and 82% of SaO_2 to be divided into three parts, at the end of the protocol on all the subjects recruited, it is expected to have:

- At least 67 measurements between 98% and 93% of SpO₂;
- At least 67 measurements between 92% and 87% of SpO₂;
- At least 67 measurements between 86% and 82% of SpO₂

In the event that this minimum target is not reached to meet the requirements of the EN 80601-2-61 standard, it may be necessary to recruit up to 2 additional subjects.

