17.3 DATA PROCESSING

Subject's data from the paper CRF will be entered manually on an electronic clinical database.

Measurements obtained with the reference device and with BrOxy M will be accessed by the Sponsor Data Manager, and processed as follows. After data acquisition from the devices, first 8 valid paired assessments of SpO_2 and HR will be selected from each plateau as follows:

- Reference device: SpO₂ and HR valid values will be selected starting from at least 30" after plateau stabilization, with a time interval between measurements of at least 20".
- BrOxy M: SpO₂ and HR values generated by BrOxy M will be obtained by processing the
 photoplethysmographic signals generated by the device with the BrOxy Medical software. Then,
 SpO₂ and HR values corresponding to the same time points selected for the reference pulse
 oximeter will be chosen.

As a result, it is expected that up to 32 paired (and synchronized) measurements of SpO₂ and HR will be obtained from each enrolled subject, from the reference device and BrOxy M. Once paired measurements for SpO₂ and cardiac frequency have been obtained at the preselected time points (0, 20", 40", etc.) the list of paired observations will be merged with subject's data in the clinical database.

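### Section 17.2 excludes windows that pass the motion checks and correlates IR_AC with itself; both rules need correcting and checking against the software

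*Combined protocol and SAP*

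**What the plan says.** Section 17.2 is the only place where a valid measurement is defined. It requires adequate signal quality and, on motion, "No movement above predefined threshold for both the reference and BrOxy M".

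The motion algorithm has three steps:
- Point 1: the amplitude of the alternating red and infrared signals "must not exceed a threshold determined empirically".
- Points 2a and 2b: the correlation of the accelerometer modulus with the red signal, and with the infrared signal, "is less than a certain threshold derived empirically".
- Step 3: "If the conditions in point 1 and 2 occur, the time window from which to derive heart rate and SpO_2 data is excluded".

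The section closes by saying that "once all the above conditions are verified, the values of SpO_2 and HR are calculated for the signal windows considered", subject to plausibility limits on HR (40 to 280 bpm) and SpO2 (80 to 100%).

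The fourth quality-control condition reads: "the correlation coefficient calculated between IR_AC and IR_AC has to be higher than the empirically determined threshold". RED_AC is defined in the first condition and used beside IR_AC in the third, but is absent from the fourth.

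Section 17.3 then applies the definition: "first 8 valid paired assessments of SpO_2 and HR will be selected from each plateau". Section 10.5 uses it to decide which data are kept from an interrupted session.

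**The concern.** Points 1, 2a and 2b all describe the absence of motion, yet step 3 removes the window when they hold. The definition and the closing rule of the same section say the opposite. In the fourth quality condition a signal is compared with itself, so the condition cannot fail.

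At stake is which readings form the primary data set. The signals are processed on the sponsor's side with the manufacturer's own software (Sections 5.2, 11.4 and 17.3), so the written rule is the plan's standard for judging whether pairs were selected as specified. While the text contradicts itself on motion, the software's selection logic cannot be checked against it.

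The two defects differ in visibility. An inverted motion rule would show up as heavy data loss. A fourth check that rejects nothing leaves no such trace.

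**Working it through.** **The plan's own count.** 10 subjects × 4 plateaus × 8 readings = 320, which matches Section 10. The minimum of 200 is in Section 3.

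**Motion rule.** Each of points 1, 2a and 2b is either met (1) or not met (0):

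| 1 | 2a | 2b | Literal step 3 | Definition and closing rule |
|---|---|---|---|---|
| 1 | 1 | 1 | exclude | accept |
| 1 | 1 | 0 | keep | reject |
| 1 | 0 | 1 | keep | reject |
| 1 | 0 | 0 | keep | reject |
| 0 | 1 | 1 | keep | reject |
| 0 | 1 | 0 | keep | reject |
| 0 | 0 | 1 | keep | reject |
| 0 | 0 | 0 | keep | reject |

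The two columns disagree in 8 of 8 rows. No row is both kept by step 3 and accepted by the closing rule.

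Simply reversing step 3 does not settle the rule, because it joins points 1 *and* 2. Excluding a window only when both points fail still disagrees with the closing rule: in 4 of 8 rows if one high correlation is enough to fail point 2, and in 6 of 8 if both must be high. Excluding when any condition fails agrees in 8 of 8.

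**Counts if the software followed the text.** The documents give no motion share, so m = 2% to 30% is assumed, with one window per reading. The definition keeps 320 × (1 − m); literal step 3 alone keeps 320 × m.

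| m | Definition | Literal step 3 |
|---|---|---|
| 2% | 314 | 6 |
| 5% | 304 | 16 |
| 10% | 288 | 32 |
| 20% | 256 | 64 |
| 30% | 224 | 96 |

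With step 3 and the closing rule applied together, 0 remain at every m. For literal step 3 to reach 200, m would have to be 200/320 = 62.5%. With the 2 extra subjects there are 12 × 32 = 384 windows, and literal step 3 keeps 8 (m = 2%) to 115 (m = 30%). The break-even is then 200/384 = 52.1%.

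**Replacement within a plateau.** Eight readings 20 s apart span 7 × 20 = 140 s of a 150 s plateau, so there is almost no room to replace an excluded reading.

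**Fourth quality condition.** The correlation of a varying signal with itself is 1, so the condition passes at every threshold below 1. For illustration, two simulated channels sharing one pulse wave, with increasing independent noise, had a red–infrared correlation of 1.00, 0.66, 0.13 and 0.00. The infrared self-correlation stayed at 1.00 throughout. The noise levels were chosen for illustration and do not describe this device.

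**The case against.** The strongest reply is that both are drafting or translation slips with a recoverable intent. The definition, the stated purpose of the motion algorithm and the closing rule all agree; only step 3 is reversed. The checks run automatically, so nobody applies the sentence by hand. Software that discarded still windows would be caught by the real-time signal check (Section 10.5), the rehearsal runs (Section 13), the set-up subject or the count after 10 subjects. Participants are seated and asked to keep still. Under the intended rule, the assumed range leaves 224 to 314 pairs, always above 200. The fourth condition is one check among several. The thresholds are not given in any case, so correcting two sentences would not make the software fully verifiable.

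Much of this stands. The low counts are conditional and would probably not survive to analysis. No error in the results is shown. The tight plateau timing applies under the correct rule too. The other quality, motion and plausibility limits still operate, so the number of poor windows admitted by the fourth condition is unknown.

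It does not remove the point. Intent does not settle whether failing one motion check or both excludes a window, and the wrong choice would admit motion without conspicuous loss. Missing threshold values do not prevent a check of the logic.

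**Conclusion.** The concern holds: the rule is wrong as written and should be corrected. That step 3 contradicts the rest of Section 17.2, and that the fourth quality condition is vacuous, follow from the wording alone, and nothing elsewhere in the document corrects either.

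The effect on the data is conditional on the software following the literal text and on the assumed motion share. In that case literal step 3 leaves 6 to 96 of 320 pairs, or none when combined with the closing rule, against a minimum of 200. The fourth condition rejects no window at any threshold below 1. What the software actually does is not known from the documents.

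**What to change.** 1. Reword motion step 3 so that a window is excluded if point 1 is not met **or** either correlation in point 2 is not met. Of the readings compared, only this one agrees with the closing rule of Section 17.2 in every combination.
2. Correct the fourth quality condition to name two different channels. RED_AC and IR_AC are the most plausible pair, since both are defined and used together in the preceding condition; the sponsor should confirm.
3. Check the implemented BrOxy software against the corrected text, including the either/both question, and document the result before the first analysable subject is processed. Resolve any difference between text and software before that point.

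The cost is two corrected sentences and one documented software check. No new data or subjects are needed.

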7.2 ENDPOINTS

The **primary endpoint** of the study will be a comparison of the accuracy of SpO_2 and HR measurements obtained with BrOxy M with that obtained with the reference pulse oximeter in paired observations over a range between 80% and 100% SpO_2 .

For each subject, four different saturation plateaus will be set up (i.e. at 97%, 92%, 87% and 82% SpO_2), waiting 30" before starting to keep the SpO_2 level on each plateau for 2.5' in order to obtain 8 measurements in post-processing. These measurements will be at least 20" away from each other, for a total of 32 measurements for each subject, as summarized in Table 1.

The study will follow the procedures described in the standard ISO 80601-2-61:2017 "Medical electrical equipment - Part 2-61: particular requirements for basic safety and essential performance of pulse oximeter equipment".

As **secondary endpoints**, the following will be verified:

• whether any relation exists between the accuracy of BrOxy M for both SpO₂ and HR and subject skin pigmentations as measured with the Fitzpatrick scale.

Clinical Investigational Plan			
Protocol No.:	Version 1.0	Page 22 of 45	
01M2020-CH.LMD	Date: 22 December 2020	1.80 == 0. 10	

• that no adverse events related to the use of BrOxy M, besides a temporary slight skin irritation of the wrist, will occur.

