- Bland -Altman (B&A) plot, to evaluate the agreement between experimental and standard values; the B&A plot analysis is a simple way to evaluate a bias between the mean differences, and to estimate an agreement interval, within which 95% of the differences of the second method, compared to the first one, fall. Data can be analyzed both as unit differences plot and as percentage differences. The Bland-Altman chart is a scatterplot with the difference of the two measurements for each sample on the vertical axis and the average of the two measurements on the horizontal axis. Three horizontal reference lines are superimposed on the scatterplot one line at the average difference between the measurements, along with lines to mark the upper and lower control limits of plus and minus 1.96*the standard deviation of the measurement differences. Bland and Altman also discuss the option of using confidence interval bounds, based on the standard error of the mean, for the upper and lower reference lines. If the two methods are comparable, then differences should be small, with the mean of the differences close to 0, and show no systematic variation with the mean of the two measurements. 'Small' would be an amount that would be clinically insignificant for the factor being measured.

Clinical Investigational Plan			
Protocol No.:	Version 1.0	Page 36 of 45	
01M2020-CH.LMD	Date: 22 December 2020		

• Linear regression analysis: to give further information about any potential proportional bias about the mean differences and averages. It is a simple test for a linear trend, with the mean difference as dependent variable and the average difference as independent. The aim is to evaluate if the mean difference can be predicted from the average. The resulting coefficients indicate whether one can accept the null hypothesis that there is no proportional bias.

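### Section 17.2, read naturally, accepts BrOxy M values only within 80–100% SpO2 and 40–280 bpm, so pairs can be excluded on the test device's own reading

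*Combined protocol and SAP*

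**What the plan says.** Section 17.2 defines a valid measurement by two numbered conditions, signal quality and absence of movement, each required of both devices. The first reads "Signal compliant with quality control for both the reference and BrOxy M". It then describes filters on red, infrared and accelerometer signals. Once these are passed, SpO2 and HR "are calculated for the signal windows considered". The next sentence is "These values are considered acceptable if the following conditions occur at the same time", followed by HR 40–280 bpm and SpO2 "values between 80 and 100" per cent.

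Section 17.1 lists what each device stores. For BrOxy M it is "The recorded values of the red and infrared sensors integrated in BrOxy M", plus accelerometer values. For the reference it is finished SpO2 and HR values with time stamps.

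Section 17.3 selects the "first 8 valid paired assessments" of SpO2 and HR from each plateau. Its reference bullet speaks of valid values. Its BrOxy M bullet only matches values to the reference time points.

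Section 7.2 sets the primary endpoint "in paired observations over a range between 80% and 100" per cent SpO2 without saying which device defines the range. Section 3 uses the reference display to check the plateau level. Table 1 puts the lowest plateau at 80–84%, target 82%. In section 16.3.2 the Bland-Altman plot carries "lines to mark the upper and lower control limits of plus and minus 1.96*the standard deviation of the measurement differences".

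**The concern.** If a pair is kept only when the BrOxy M reading lies within 80–100%, inclusion depends on the error being measured. On the lowest plateau the floor of 80 is close to the reference value. At reference 82, a BrOxy M error of −3 or lower removes the pair, while over-readings there stay. At that plateau this moves the mean difference upward and narrows its SD, whatever the device's bias.

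The paired t test, correlation, CCC, Bland-Altman limits and proportional-bias regression in 16.3.2 would all use the filtered pairs. HR is part of the primary endpoint, and because both conditions must hold together, an SpO2 reading below 80 also costs the HR pair. No section provides an analysis that retains the rejected pairs or a count of them.

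**Working it through.** **Which device the window tests.** The range applies to values calculated from signal windows. Only BrOxy M values arise that way (17.1, 17.3); section 6 also says the reference downloads recorded SpO2 and HR. If the window applied to both devices, the pair would still depend on the BrOxy M reading. Only a reference-only window avoids this, and no section states one.

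**Planned count.** 10 subjects × 4 plateaus × 8 = 320 pairs, 80 per plateau. This matches the total in 16.2.

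**Room for replacement.** A plateau lasts 150 s. At 20 s spacing the points are 0, 20, …, 140 s, which is 8. On the preselected grid in 17.3 a dropped point is not replaced. Under the looser wording (at least 20 s apart) the remaining 10 s gives some slack. Replacement would not remove the selection, and nor would the up to 2 extra subjects, who pass through the same filter.

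**Assumptions, not in the documents.** Reading = reference + bias b + Normal(0, SD), rounded to an integer; references at the four targets; equal weights; b = 0, −2, +2; SD = 2, 3. Output is either capped at 100 or not, since the documents do not say. Rounding gives an unfiltered SD of √(4 + 1/12) = 2.02 or √(9 + 1/12) = 3.01.

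**Lowest plateau, reference 82.** Share dropped = Φ((79.5 − 82 − b)/SD).
- b = 0, SD 2: Φ(−1.25) = 10.6% (8.5 of 80); mean 0.00 → +0.42; SD 2.02 → 1.69
- b = 0, SD 3: Φ(−0.83) = 20.2% (16 of 80); mean 0.00 → +1.07; SD 3.01 → 2.29
- b = −2, SD 2: Φ(−0.25) = 40.1% (32 of 80); mean −2.00 → −0.68; SD 2.02 → 1.29
- b = −2, SD 3: Φ(−0.17) = 43.4% (35 of 80); mean −2.00 → +0.10; SD 3.01 → 1.90
- b = +2, SD 2 or 3: 1.2% or 6.7%; mean +2.00 → +2.07 or +2.42

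For b = 0, SD 2 the loss is 40.1% at reference 80 and 1.2% at reference 84. With unrounded readings at reference 82 it is 80 × Φ(−1) = 12.7 of 80.

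**Highest plateau, reference 97, only if output can exceed 100.** Share dropped = 1 − Φ((100.5 − 97 − b)/SD): 4.0% or 12.2% for b = 0, and 22.7% or 30.9% for b = +2 (SD 2 or 3).

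**Pooled, 320 pairs.** This is the analysis that 16.3.2 describes. Half-width = 1.96 × SD.

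| b, SD | Capped: dropped; mean; half-width | Not capped: dropped; mean; half-width |
|---|---|---|
| 0, 2 | 2.6%; −0.01 → +0.08; 3.91 → 3.78 | 3.6%; 0.00 → +0.05; 3.96 → 3.75 |
| 0, 3 | 5.2%; −0.06 → +0.17; 5.72 → 5.47 | 8.3%; 0.00 → +0.07; 5.91 → 5.45 |
| −2, 2 | 10.1%; −2.00 → −1.78; 3.96 → 3.86 | 10.2%; −2.00 → −1.78; 3.96 → 3.85 |
| −2, 3 | 11.7%; −2.01 → −1.61; 5.85 → 5.61 | 12.5%; −2.00 → −1.66; 5.91 → 5.57 |
| +2, 2 | 0.3%; +1.90 → +1.92; 3.75 → 3.71 | 6.0%; +2.00 → +1.85; 3.96 → 3.78 |
| +2, 3 | 1.7%; +1.80 → +1.90; 5.52 → 5.36 | 9.8%; +2.00 → +1.78; 5.91 → 5.50 |

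The half-width falls in all 12 cases, by about 1–8%. The loss runs from 0.3% × 320 ≈ 1 to 12.5% × 320 = 40 pairs. The mean moves between −0.22 and +0.40.

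**The case against.** The text is less definite than the natural reading suggests. The window is not one of the two numbered conditions, the wording is *acceptable* rather than *valid*, and no sentence says that an out-of-range value is deleted. The bullets in 17.3 attach *valid* to the reference only. Section 17.2 is also loosely drafted: read literally, motion step 3 excludes the windows that pass steps 1 and 2, and one quality check correlates IR_AC with itself. This stands as a reason for caution. It does not establish a reference-only window, because the range follows values calculated from signals, 17.2 demands validity of both devices, and 17.3 opens with valid pairs.

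It can also be said that 80–100% is simply the study range. That range can be held by the reference value, which already sets the plateau level.

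On size, 16.3.2 plans no per-plateau analysis, so the large losses at reference 82 are not what the study would report; the 40% figures also need an assumed bias of −2. The pooled effect is modest. Nor does the filter always flatter the device: at reference 80 with bias +2, the root mean square difference rises from 2.84 to 2.95 (SD 2) or from 3.62 to 3.83 (SD 3). All of this stands.

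Finally, the range check may sit inside the software, in which case rewording alone will not recover the values. The documents do not settle this, and the fix has to allow for it.

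**Conclusion.** The point holds as a selection problem on the natural reading of 17.2: pairs can be excluded according to the BrOxy M reading, and no section limits the window to the reference. Whether selection occurs does not depend on the assumed errors; its size does. Under the assumptions above, the pooled limits narrow by about 1–8%, the pooled mean moves by up to about 0.4 points in a direction that depends on bias and capping, and 1 to 40 of 320 pairs are lost together with their HR values.

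A reader might infer that the plan expressly deletes BrOxy M readings outside the range, or that the study's conclusion would change. The documents support neither. The device is unnamed, and with no BrOxy M bias, SD or accuracy limit stated, no change from fail to pass can be shown. A reader might also take the plateau-level shifts as the expected bias of the reported result; the pooled figures are the relevant ones.

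The effect is modest, but it is avoidable and should be corrected before the recordings are processed. Confidence is medium because the wording is ambiguous.

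**What to change.** In 17.2:
- State that the 80–100% SpO2 range applies to the reference value only.
- State that every BrOxy M SpO2 value passing the signal-quality and motion checks is kept as the software reports it, including values below 80% or above 100%.
- Treat HR alike: apply 40–280 bpm to the reference HR only. If it is retained for BrOxy M as an artefact check, let it remove only the HR value, and report how many.
- State that an SpO2 or HR range failure on BrOxy M does not remove the other parameter's pair.
- If the software itself suppresses out-of-range values, report them as missing because out of range.

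Add a table of pairs removed by each check, per plateau.

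The cost is a few sentences and one table, plus a check of how the software handles out-of-range values. No extra subjects or measurements are needed. The downside is that reported agreement, mainly at the lowest plateau, may look slightly less favourable.
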